Approximately 30 patients are considered sufficient to explore the study objectives and will be included in this study (number of patients may be increased if there is benefit observed in initial cohort of patients. There is no formal sample size calculation estimated).

Method of assigning patient to treatment group:

All eligible patients entering into the study will be randomized in 2:1 ratio to receive the treatment A/ B respectively. A computer derived randomization schedule is planned to be generated using appropriate system e.g. SAS to assign patient to treatment groups. Randomization will be central and appropriate system (e.g. remote telephone based, computer-based email, sealed envelope) will be used to distribute randomization schedule to the site

Note: If the patient is randomised to Arm A and is not initiated itolizumab or not administer one full infusion, is then not considered randomized. The same randomisation code will be used for the subsequent subject in that particular site.

Approximate number of sites:

1-10 sites

7. Treatment

Treatment Intervention and Dose:

Arm A: Best supportive care + Itolizumab

The best supportive care to be given as per the institutions protocol will be administered

(e.g: antivirals /antibiotics/ hydroxychloroquine; oxygen therapy, etc) + **Itolizumab**

Itolizumab

Note: Premedication: Hydrocortisone 100 mg i.v (or equivalent short acting glucocorticoid) and Pheniramine 30 mg per i.v. about 30 ± 10 minutes prior to infusion.

Start at 1.6 mg/kg dose iv infusion, if well tolerated, investigator has the discretion to continue with 1.6 mg/kg dose every 2 weeks or 0.8 mg/kg weekly regimen.

Subsequent dose and frequency can be modified, deferred or stopped if patient recovers as per investigator's discretion. If patients' overall parameters improve (if performed and RT-PCR is negative) further dose need not be given. Total infusion received during study duration can vary from 1 to 4 for each patient.

Arm B: Best supportive care

The best supportive care to be given as per the institutions protocol will be administered

(e.g: antivirals/antibiotics/ hydroxychloroquine; oxygen therapy, etc)

Dosing, Handling and Storage of Itolizumab

- Itolizumab is to be stored in 6R, USP type-1, 10 mL glass vials, refrigerated condition at 2°C to 8°C and is stable at that temperature for 36 months.

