Source data is all information, original records of clinical findings, observations, or other activities in a clinical study necessary for the reconstruction and evaluation of the study. Source data are contained in source documents. Examples of these original documents, and data records include: hospital records, clinical and office charts, laboratory notes, memoranda, subject's diaries or evaluation checklists, pharmacy dispensing records, recorded data from automated instruments, copies or transcriptions certified after verification as being accurate and complete, microfiches, photographic negatives, microfilm or magnetic media, x-rays, subject files, and records kept at the pharmacy, at the laboratories, and at medico-technical departments involved in the clinical study.

Location of Data

All records and documents pertaining to the study will be maintained in the permanent files of the Investigator and will be available for inspection by the authorized party at any time.

Statistical Analysis

In general, continuous variables is summarized using descriptive statistics such as mean, standard deviation, 95% confidence interval (CI), minimum, and maximum. Categorical variables are summarized using proportions (counts and percentages). All statistical tests will be performed at 5% level of significance (two-sided test) and p-value<0.05 considered statistically significant (if necessary). All statistical analysis will be performed using SAS® (version 9.4 or higher) system software (SAS Institute Inc., USA)/or R/or EAST/or NCSS software.

11.Administrative Procedures

Ethics and Good Clinical Practice

This research will be carried out in accordance with the clinical research guidelines established by the basic principles defined in the revised New Drugs and Clinical Trials 2019, India and the principles enunciated in the Declaration of Helsinki [Ethical Principles for Medical Research Involving Human Subjects, revised, October 2013]. The investigator is responsible for overall activities at the center in accordance with Indian ICH-GCP guidelines, current New Drugs and Clinical Trials 2019 and ethical guidelines for biomedical research on human subjects issued by ICMR.

Interim study report - Data will be provided to DSMB (constituted prior to first patient screened) on a periodic basis. Based on DSMB recommendation, interim clinical study report may be prepared and submitted to DCGI/regulatory agencies.

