## **4 TRIAL DESIGN AND DESCRIPTION**

### **4.1 Trial Design**

It is a Multi-Centric, Open label, Two Arm Randomized, Pivotal Phase 2 Trial to Study the Efficacy and Safety of Itolizumab in COVID-19 complications. Patients who have tested positive for virological diagnosis of SARS-CoV2 infection (PCR) are planned to be randomised for enrolment from various centres in India. All eligible patients entering into the study will be randomized in 2:1 ratio to receive the treatment A/ B respectively.

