## **6 General Aspects for Statistical Methods**

In general, metric variables and derived parameters will be presented using descriptive summary statistics including arithmetic mean, standard deviation, median, minimum and maximum.

Categorical variables will be presented using descriptive summary statistics including number of patients and percentages. Percentages of patients will be based on non-missing values. The presentation will be by treatment group. Individual values as well as minimum and maximum will be presented with the same number of decimal places as the raw data. Derived parameter will have as many decimal places as the measured number with the smallest number of decimal places. Descriptive statistics, such as arithmetic/geometric mean and median will be presented with an additional decimal place and standard deviation with two additional decimal places as the raw or derived data. All relevant subject data will be included in the listings; and all subjects entered into the database will be included in subject data listings. SAS 9.4 or any other validated software will be used for analysis purpose and generating Tables, Listings & Figures. P-values less than 0.05 may be reported as statistically significant.

The formatting of the final version of a table, figure, or listing may differ from what is presented in the mock shell or the presentation of the results may be changed, however the key content will remain unchanged. Additional tables, figures, and listings may be generated to supplement the planned output.

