## **9 Efficacy Evaluation**

### **Primary Efficacy Evaluation**

Proportion of patients with deterioration of lung function as measured by Stable SpO2 without increasing FiO2 and Stable PaO2 without increasing FiO2 will be summarized using count and

percentage. The difference between two proportion with its 95% Confidence interval and associated p-values may be presented, if p-value is less than 0.05 it can be concluded that there is a statistically significant difference between two proportions.

Reduction of endo-tracheal intubation rate, measured as rate of patients needing intubation will be summarize using descriptive statistics.

Reduction in proportion of patients who need/ Non-invasive ventilation / Invasive mechanical ventilation/high flow nasal oxygen will be summarized using count & percentage.

One-month mortality rate between the two arms will be summarized. The difference between two rates with its 95% Confidence interval and associated p-values may be presented, if p-value is less than 0.05 it can be concluded that there is a statistically significant difference between two-rates.

Change in inflammatory markers like CRP (C-reactive protein) level, d-Dimer, ferritin etc will be summarize with descriptive statistics. Change from Baseline may be presented along with 95% CI.

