### **13 Programming Considerations, Listing of Tables, Figures & Format, Software detail**

All tables, data listings, figures (TLFs), and statistical analyses will be generated using SAS® for Windows, Release 9.4 (SAS® Institute Inc., Cary, NC, USA) or any other validated statistical software. One SAS program will be used to create several outputs / a separate SAS program will be created for each output. Output files will be delivered in Word / pdf format.

For few assessments (weight, physical examination, vital signs haematology, biochemistry Chest X Ray/CT scan), screening assessments will be considered as baseline assessment (as day 1).

Missing data:

All attempts will be made to collect all data per protocol. Any data point that appears to be erroneous or inexplicable based on clinical judgment will be investigated as a possible outlier. If data points are identified as outliers, sensitivity analyses may be performed to examine the impact of including or excluding the outliers. Subjects who meet fatal outcome during the observing period up to 30 days will be an event. Subjects lost to follow up or withdraw consent during the observing period, will be censored at last assessment. Patient data will be censored at the time of their last observed assessment in case of lost to follow up, withdrawal consent or after 30 days of enrolment.

Following Rules may be applied for the derivation of efficacy endpoints

- Patients who discharged from hospital (with improvement, Off O2), the status at discharge will be carried forward.
- Patients who lost to follow up will be considered as Non evaluable (NE)
- Patients who worsen or met fatal outcome, status at event will be carried forward.

Note: Telephonic improvement of weaning of O2 will be considered as improved.

These rules will be applied to analyse following endpoint:

Proportion of patients with deterioration of lung function as measured by:

- Stable SpO2 without increasing FiO2
- Stable PaO2 without increasing FiO2

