## 14.2 Primary outcome measures

### 14.2.1 Primary Outcome Measures

Visit*		Arm A (N=XX)	Arm B (N=XX)
Baseline	patients with Stable SpO2 without increasing FiO2	XX (XX.X %)	XX (XX.X %)
	patients with Stable PaO2 without increasing FiO2	XX (XX.X %)	XX (XX.X %)

\*day 7, day 14, day 21 and day 30/EOS or all available visits

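### SAP 9 permits an unadjusted p<0.05 conclusion for the lung-function proportions and for one-month mortality, with no named test, no multiplicity rule and no decision visit for the lung measures

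*SAP*

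**What the plan says.** SAP 9, Primary Efficacy Evaluation, attaches a decision rule to two items. For the proportions based on stable SpO2 and stable PaO2: "if p-value is less than 0.05 it can be concluded that there is a statistically significant difference between two proportions". For one-month mortality: "if p-value is less than 0.05 it can be concluded that there is a statistically significant difference between two-rates". In both cases the difference, its 95% CI and the p-value are optional outputs. The other primary outcomes in that section are descriptive.

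SAP 6 adds a general permission: "P-values less than 0.05 may be reported as statistically significant". The Statistical Analysis text in Protocol section 10 sets a two-sided 5% level for all tests, to be applied if needed. So sidedness is given. The test, the CI method, any order of testing and any multiplicity rule are not.

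The shells differ from each other. Shell 14.2.1 gives stable SpO2 and stable PaO2 a row each, repeated over "day 7, day 14, day 21 and day 30/EOS or all available visits"; it has no p-value row and no CI row. Shell 14.2.7, for mortality, has both. Mortality has a fixed time point; the lung measures do not.

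SAP 4.1 describes a "Multi-Centric, Open label, Two Arm Randomized, Pivotal Phase 2 Trial". Protocol section 6 and SAP 4.5 say "Approximately 30 patients are considered sufficient to explore the study objectives", with no formal sample size calculation.

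**The concern.** SAP 9 states a rule for drawing a conclusion, so this is more than an omission. As written, a significant difference may be concluded from SpO2 stability, PaO2 stability or mortality, by any test for two proportions, and for the lung measures at any visit. In an open-label trial of about 30 patients, those choices could be made after the results are known. A reader of the report could then not tell a pre-planned finding from a selected one.

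Two things are at stake. First, with groups this small, common tests of the same table can fall on opposite sides of 0.05. Second, if any one significant result were offered as evidence of benefit, the chance of a false claim could exceed the nominal level.

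**Working it through.** **1. Inputs.** N is about 30, randomised 2:1 (Protocol 6, SAP 4.5): 30 × 2/3 = 20 in Arm A and 10 in Arm B. The level is two-sided 5% (Protocol 10). Neither document gives event rates, correlations, an effect size or power, so there is no planned figure to reproduce. Step 2 needs no assumed rate; steps 3 to 5 do.

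**2. Does the unnamed test matter?**
- 0/20 v 2/10 deaths, Fisher: the probability that both deaths fall in Arm B is C(10,2)/C(30,2) = 45/435 = 0.103. The other two tables with two deaths are more likely (200/435 and 190/435), so the two-sided p is 0.103.
- Same table, uncorrected chi-square: pooled rate 2/30; SE = √[0.0667 × 0.9333 × (1/20 + 1/10)] = 0.0966; z = 0.20/0.0966 = 2.07; p = 0.038.
- 0/20 v 3/10, Fisher: C(10,3)/C(30,3) = 120/4060, p = 0.030. With Yates' correction: 30 × (60 − 15)²/(20 × 10 × 3 × 27) = 60750/16200 = 3.75, p = 0.053.
- 3/20 v 5/10: Fisher p = 0.078, uncorrected chi-square p = 0.041.
- Of all possible 20 v 10 tables, 12 are significant by uncorrected chi-square but not by Fisher.

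**3. Several measures, one visit each.** Trials were simulated with no drug effect, counting those with at least one two-sided p<0.05 in either direction. Assumed lung/death rates were 20/10, 30/15, 40/25 and 50/35%, with latent correlation 0.5, 0.7 or 0.9 (12 scenarios).

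| Measures | Fisher | Uncorrected chi-square |
|---|---|---|
| SpO2, PaO2 and mortality | 4.6-8.3% | 8.8-13.8% |
| One combined lung measure and mortality | 3.1-5.8% | 6.6-9.6% |

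A single test at rates of 10-50% has exact size 1.3-3.3% (Fisher) or 3.4-5.2% (chi-square). This conservatism is why the Fisher totals stay close to 5%.

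**4. One lung measure, four visits.** Assumed rates were 20-50% and adjacent-visit correlation 0.7-0.9. Either no patients, or half of them, had their status fixed from the second visit on, to mimic the carry-forward in SAP 13 ("Patients who discharged from hospital (with improvement, Off O2), the status at discharge will be carried forward").

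| Visit | Fisher | Uncorrected chi-square |
|---|---|---|
| One fixed visit | 2.2-3.1% | 3.7-5.2% |
| Any of four | about 5.5-11% | about 9-17% |

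The ranges include the carried-forward scenarios, so carry-forward does not remove the effect.

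**5. Power if mortality is the one tested comparison.** Exact enumeration with Fisher, results favouring Arm A, assumed death rates A v B: 23% (10 v 30%), 39% (5 v 30%), 42% (10 v 40%), 61% (5 v 40%).

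**The case against.** The strongest reply is that the plan is softer than its decision sentences suggest. The p-values are optional, the sample is described as enough to explore, and the only planned efficacy shell with a p-value is mortality, which has a fixed time point. SAP 6 and 13 say the key content of the shells will not change. This stands, and it narrows the point to optional text that its own shell does not match. It does not remove the point: the same sections allow additional tables, the permission to conclude is express, the trial is labelled pivotal, and the mortality p-value that is planned still has no named test.

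SAP 9 can also be read as one combined lung endpoint. The two-row shell points the other way, but the text does not settle it. On the combined reading there is little excess error with Fisher.

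Three stronger readings are tempting, and the documents do not support them:
- That one significant result makes the trial positive. No section says so, and none excludes it.
- That the error is 1 − 0.95³ = 14.3%, or 1 − 0.95⁹ = 37.0% for two lung measures at four visits plus mortality. Those figures assume independent tests of exact 5% size. Here the outcomes would be correlated and Fisher is conservative. Nor does any text authorise picking a visit; a table that reports every visit would make selection visible, though nothing prevents it.
- That enlarging the trial on observed benefit (SAP 4.5) inflates the error by itself. By a normal approximation, one test at the final N gives at most 2.5% in favour of Arm A. The figure reaches 4.1% (30 patients raised to 60) only if a result at 30 may also be claimed, and the plan does not say that it may.

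**Conclusion.** The point holds in limited form. SAP 9 permits an unadjusted significance conclusion for the lung-function proportions and for mortality, without a test, an order or a multiplicity rule, and without a decision visit for the lung measures. The lung shell does not match that text.

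The firm part is the unnamed test: at 20 v 10 it can reverse the mortality conclusion, whatever the true rates. The error-rate part is conditional. It applies only if any significant result is used as evidence of benefit, and it rests on assumed rates and correlations. Its size runs from little or no excess (Fisher, one combined lung measure, or low rates) to about 14% (chi-square, three measures), or about 17% if a lung visit were also chosen freely. The amendment should be made because it is cheap, but the defect does not by itself invalidate the trial.

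**What to change.** Amend the SAP as early as possible, before those who choose have reviewed any comparative data, and at the latest before database lock (SAP 1 allows this). Because the trial is open-label, record the date of the choice and what data those choosing had seen.

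- **SAP 9:** apply the p<0.05 conclusion only to one-month mortality, the one comparison whose shell already carries a p-value. Define it as death from any cause by Day 30, tested by a two-sided Fisher's exact test. State how patients lost before Day 30 are handled, consistently with the censoring in SAP 13.
- **SAP 3.2.1 and Protocol 5:** correct the mortality definition, which at present describes survivors.
- **Lung proportions:** delete the significance sentence. Say whether they are two measures or one, report differences with 95% CIs at every visit without a significance claim, and add those rows to shell 14.2.1.
- **Alternative:** delete both significance sentences and label all p-values descriptive.
- **Either way:** align SAP 6 and the Statistical Analysis text in Protocol 10.
- **Minor addition, SAP 4.5 and 11:** if N is increased, test efficacy once, at the final N, with no significance claim from the first 30 patients or from an interim report.

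The cost is wording. Fewer outcomes can be called significant, and the mortality test keeps the low power shown above. The descriptive option gives up the significance claim altogether.

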## 3.2 Outcome Measures

### 3.2.1 Primary endpoint

1. Proportion of patients with deterioration of lung function as measured by\*:
  - Stable SpO2 without increasing FiO2
  - Stable PaO2 without increasing FiO2
2. Reduction of endo-tracheal intubation rate, measured as rate of patients needing intubation\*
3. Reduction in proportion of patients who need\*
  - Non-invasive ventilation
  - Invasive mechanical ventilation
  - High flow nasal oxygen
4. Time of duration of mechanical ventilation or time to end of mechanical, measured as elapsed time from the start date of mechanical ventilation to the weaning date, for patients needing intubation\*
5. One-month mortality rate between the two arms\* [ Time Frame: up to 1 month ] 1-month mortality is defined as the ratio of patients who will live after 1 month from study start out of those registered at baseline
6. Change in inflammatory markers like CRP (C-reactive protein) level, d-Dimer, ferritin etc. [ Time Frame: Arm A; baseline, during treatment (Before every dose and 12 to 24 h after every dose) up to 1 month, Arm B: baseline, 12 to 24 h and approx. 7 and 14 days after randomization ]

\* Applicable for both the arm

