### 14.2.2 Proportion of patients needed intubation during the study

	Arm A (N=XX)	Arm B (N=XX)
Patients needed intubation n(%)	XX (XX.X %)	XX (XX.X %)

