### 14.2.7 One-month Mortality Rate

	Arm A [n (%)]	Arm B [n (%)]
Number of patients died	XX (XX.X %)	XX (XX.X %)
95% CI Difference between Rate	XX (XX , XX)	
p-value	XX	

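### Intubation is a primary endpoint defined as a reduction, but no between-arm difference with an interval is prespecified for it

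*SAP*

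**What the plan says.** Protocol section 5 and SAP section 3.2.1 list as primary outcome 2 "Reduction of endo-tracheal intubation rate, measured as rate of patients needing intubation", marked as applying to both arms. Neither states what the reduction is measured against.

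For its analysis, SAP section 9 (Primary Efficacy Evaluation) says: "Reduction of endo-tracheal intubation rate, measured as rate of patients needing intubation will be summarize using descriptive statistics". SAP section 6 explains what that means for a yes/no outcome: "Categorical variables will be presented using descriptive summary statistics including number of patients and percentages", shown by treatment group. The protocol's statistical paragraph (section 10) likewise gives categorical variables counts and percentages. Its general two-sided 5% level is not tied to intubation.

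Shell 14.2.2, titled "Proportion of patients needed intubation during the study", has the single row "Patients needed intubation n" (%), with one column per arm and no row for a difference, interval or p-value.

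For one-month mortality, the same part of SAP section 9 says: "The difference between two rates with its 95% Confidence interval and associated p-values may be presented". Shell 14.2.7 has a row labelled "95% CI Difference between Rate" and a p-value row.

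**The concern.** Exclusion criterion 5 (Protocol section 6, SAP section 4.4) keeps out anyone on invasive ventilator support. Apart from deviations, the intubation rate at entry is therefore zero in both arms and cannot fall within an arm. The only reduction the trial can show is a lower proportion intubated in Arm A than in Arm B. That contrast is the endpoint, and the plan names neither the contrast nor a measure of its uncertainty.

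At stake is how a primary clinical outcome will read in the study report. With about ten control patients, one intubation more or fewer moves the Arm B rate by ten percentage points. Two percentages side by side invite the reader to take the gap at face value. If a contrast is added later, in an open-label trial, its form will have been chosen when the data could already be known.

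**Working it through.** The plan states no intubation rate, effect size or power, so there is no figure of its own to reproduce. The check is a comparison of the plan's parts, followed by an illustration of size.

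**1. What is planned, endpoint by endpoint**

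| Outcome | Between-arm difference and 95% CI in SAP section 9 | Row for it in the shell |
|---|---|---|
| Lung function (primary 1) | Optional | None (14.2.1) |
| Intubation (primary 2) | None | None (14.2.2) |
| Invasive ventilation (in primary 3) | None | No shell for it in 14.2.2 to 14.2.6 |
| One-month mortality (primary 5) | Optional | Present (14.2.7) |

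For biomarkers, lymphocytes, CRP and the P/F ratio, the secondary part of SAP section 9 commits to a 95% interval for the treatment difference. No other section of either document plans a contrast for intubation.

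**2. Arm sizes**

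About 30 patients at 2:1 (Protocol section 6, SAP section 4.5): 30 × 2/3 = 20 in Arm A and 30 × 1/3 = 10 in Arm B. These are approximate, and the documents allow the number to increase.

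**3. Interval for a difference**

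The event counts below are assumptions, since the documents give none. The Newcombe interval combines the Wilson limits (l, u) of each arm. With d = pA − pB:

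- lower = d − √[(pA − lA)² + (uB − pB)²]
- upper = d + √[(uA − pA)² + (pB − lB)²]

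Wilson 95% limits: 2/20 gives 0.028 to 0.301; 0/20 gives 0 to 0.161; 3/10 gives 0.108 to 0.603.

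*2/20 against 3/10:* d = 0.10 − 0.30 = −0.20.
- lower = −0.20 − √[(0.100 − 0.028)² + (0.603 − 0.300)²] = −0.20 − 0.312 = −0.512
- upper = −0.20 + √[(0.301 − 0.100)² + (0.300 − 0.108)²] = −0.20 + 0.278 = +0.078

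*0/20 against 3/10:* d = −0.30.
- lower = −0.30 − √[0² + (0.603 − 0.300)²] = −0.30 − 0.303 = −0.603
- upper = −0.30 + √[0.161² + (0.300 − 0.108)²] = −0.30 + 0.251 = −0.049

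**4. Range over several assumed outcomes**

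| Arm A | Arm B | Difference (points) | Newcombe 95% CI |
|---|---|---|---|
| 1/20 | 2/10 | −15 | −46.3 to +8.5 |
| 2/20 | 3/10 | −20 | −51.2 to +7.8 |
| 2/20 | 4/10 | −30 | −59.6 to +0.7 |
| 4/20 | 5/10 | −30 | −58.9 to +4.1 |
| 0/20 | 3/10 | −30 | −60.3 to −4.9 |

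The intervals are about 55 to 63 points wide. Three rows share the same difference of −30 points. In one the interval excludes zero and in two it does not, so the size of the gap alone does not tell the reader what the data support.

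**The case against.** The strongest reply is that descriptive reporting is a legitimate choice here. The trial enrols about 30 patients to explore its objectives, has no formal sample size calculation, tests only if necessary, and allows additional tables. This stands in part: the omission does not make the analysis invalid. It does not answer the point, because an interval is itself a description of precision and needs no power claim. The permission for extra tables names no contrast. SAP section 4.1 also describes the trial as pivotal.

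Four stronger readings are tempting, and the documents do not support them.

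- A reader might infer that the reduction cannot be estimated at all. Shell 14.2.2 gives n and N by arm, so the difference follows by subtraction and an interval can be computed by anyone. What is missing is the prespecified contrast and its planned presentation.
- A reader might infer that the intubation table presents its percentages under the name of a reduction. Its title says proportion; only shells 14.2.3 to 14.2.6 are titled as reductions. The word attaches to intubation in the endpoint definition and the SAP section 9 text.
- A reader might infer that the other primary endpoints are firmly given intervals. For lung function the SAP says "The difference between two proportion with its 95% Confidence interval and associated p-values may be presented", the wording for mortality is equally permissive, and shell 14.2.1 has no row for a difference. Only mortality has the contrast in both places.
- A reader might extend the point unchanged to non-invasive ventilation and high-flow oxygen. Users of these can enrol, and shells 14.2.3 and 14.2.6 follow patients on the device at baseline and count those stable or improved. That is a different quantity on a different denominator, so one added row would not supply the contrast.

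**Conclusion.** The point holds in a limited form. Intubation is a primary endpoint whose meaning depends on a comparison between arms, and the plan prespecifies neither that comparison nor its interval, although it sets out both for mortality. The same gap affects invasive mechanical ventilation within endpoint 3.

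On 20 and 10 patients and the assumed counts shown, the unreported uncertainty is an interval 55 to 63 percentage points wide. The intervals need not include zero: 0/20 against 3/10 does not. So it would be wrong to infer that any intubation result from this trial must be inconclusive. The illustration rests on the approximate 2:1 split of 30 and on invented event counts. The finding about the text rests on neither.

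This is a worthwhile and nearly free improvement to the reporting of a primary endpoint. It does not show that the trial or its analysis is invalid.

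**What to change.** 1. In SAP section 9, define the reduction in intubation as the Arm A minus Arm B difference in the proportion of patients intubated by day 30.
2. In Table 14.2.2, add a row with that difference and its 95% score-type interval, naming the method (Newcombe or Miettinen-Nurminen). The layout can follow 14.2.7.
3. Present the row as estimation. Do not make a claim of reduction conditional on the interval: that would add a further 5% decision rule to the list of primary outcomes, for which the SAP has no multiplicity provision.
4. Report invasive mechanical ventilation (endpoint 3) with the same contrast, in a short shell of its own or as a second row in 14.2.2.
5. Leave the shells for non-invasive ventilation and high-flow oxygen out of this change. A whole-population contrast for them would need new tables and is a separate decision.

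The cost is one definition in SAP section 9, one row in 14.2.2, and one row or small shell for invasive ventilation. No further patients or data are needed: the listing of supportive care and oxygen therapy (16.1.12) already records intubation dates. SAP section 1 allows such a revision before database lock.
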